4.2. Safety Analysis Set (SS)

All subjects who take at least 1 dose of study drug in the RI period will be included in the Safety Analysis set (SS). Safety analyses will be based on the actual treatment a subject received.

4.3. Run-in Analysis Set (RIS)

All subjects who received at least 1 dose of study drug in the RI period will be included in the RI analysis set (RIS).

4.4. Long Term Extension Analysis Set (LTES)

All subjects who received at least 1 dose of study drug in the LTE will be included in the Long-term Extension Analysis set (LTES).

4.5. Per Protocol (PP) Analysis Set

The Per Protocol Analysis set (PP) is a subset of the ITT analysis set with the exclusion of subjects with important protocol violations or violations that may potentially bias statistical analyses or the ethical conduct of the study. The criteria of these violations will be determined prior to unblinding. This analysis set may be used for sensitivity analyses for efficacy endpoints in the RW period.

4.6. Pharmacokinetics Analysis Set

The Pharmacokinetic (PK) Analysis set includes subjects who receive at least 1 dose of study drug and have at least 1 post-baseline PK sample. The PK analysis set will be used for all PK analyses.

4.7. Verification of Analysis Sets

A blinded review to verify all defined analysis sets excluding LTES will be conducted before database lock of primary analysis. The results will be documented. The document will list subjects excluded from each analysis set with reason(s).

5. STATISTICAL METHODOLOGY

5.1. Population Characteristics

5.1.1. Study Subjects Disposition

Subject disposition will be summarized as follows.

- RI period
 - Screened Subjects (Signed Informed Consent)
 - Enrolled
 - Subjects treated in RI period
 - Subjects completed RI treatment
 - Subjects with early treatment discontinuation and reasons for treatment termination
 - Subjects with treatment ongoing at end of RI period
- RW Period
 - Number of subjects randomized, by arm
 - Subjects treated in RW period
 - Subjects who completed RW period
 - Subjects who discontinued study drug before end of RW period with reason of discontinuation
 - Subjects with treatment ongoing at end of RW period
- Number of subjects who consented to the LTE period
- LTE
 - Subjects who completed the Treatment Period

- Subjects who discontinued study drug with reasons for treatment discontinuation
- Study disposition
 - Subjects who completed
 - Subjects who terminated early and reasons for early termination
 - Subjects with study ongoing at data cutoff

5.1.2. Baseline Demographic

Frequency counts (n) and percentages (%) will be presented for sex, race, ethnicity, and age group (i.e., 12-17 years, 18-64 years, and 65 years to the maximum age in the ITT analysis set). Descriptive statistics such as number of subjects (n), mean, standard deviation, median, minimum and maximum will be presented for age (years), weight (kg), Height (cm), and body mass index (BMI) kg/m².

5.1.3. Baseline Disease Characteristics

Baseline disease characteristics include the following:

- Oral corticosteroid use at RI Baseline (yes/no)
- Diagnosis of recurrent idiopathic pericarditis at RI (yes/no)
- Type of recurrent Pericarditis
 - Idiopathic
 - Pericardiotomy syndrome
 - Dressler's syndrome
 - Still's disease
 - Other
- Duration of disease from first episode to the date of informed consent
- Total number of pericarditis episodes, total number of episodes in the past year until first injection in the RI period, and annualized number of episodes per year,
- Time since beginning of qualifying episode in days
- Baseline central CRP value and weekly pain NRS score
- Baseline pericardial rub, effusion, tamponade, electrocardiogram (ECG) findings (widespread ST-elevation and PR-Depression), ECG interpretation
- Pericarditis treatment at baseline
 - Analgesics
 - Non-opioid analgesics
 - Opioid analgesics
 - Nonsteroidal anti-inflammatory drug (NSAIDs)
 - Aspirin

- Other NSAIDs
- Colchicine
- Corticosteroids
 - Oral corticosteroids
 - IM/IV corticosteroids
- Other

Disease characteristics for the qualifying episode, including the following:

- Number and proportion of subjects with presence of pericarditis pain, pericardial rub, new widespread ST-segment elevation or PR-segment depression on ECG, new or worsening in pericardial effusion, and pericardial inflammation on magnetic resonance imaging (MRI).
- Values of pain level, CRP (mg/dL), fever (Celsius), white blood cell (WBC; $10^3/\mu\text{L}$), and erythrocyte sedimentation rate (ESR) (mm/hr).
- Treatment for the qualifying episode
 - Analgesics
 - Non-opioid analgesics
 - Opioid analgesics
 - Nonsteroidal anti-inflammatory drug (NSAIDs)
 - Aspirin
 - Other NSAIDs
 - Colchicine
 - Corticosteroids
 - Oral corticosteroids
 - IM/IV corticosteroids
 - Other

The categorical (discrete) variables will be summarized using counts and percentages. The continuous variables will be summarized using n, mean, median, standard deviation, and range (minimum, maximum). Summaries will be presented for the RI, RW, and LTE periods.

Baseline disease characteristics will also be summarized for subjects who are on corticosteroid at RI baseline. In addition to those specified above, the following baseline data will be summarized:

- Duration (in weeks) of using oral corticosteroid prior to enrollment
- Average dose (mg/day) of oral corticosteroid prior to enrollment
- Cumulative dose (mg) of oral corticosteroid prior to enrollment

5.1.4. Medical/Surgical History

Medical/Surgical history will be summarized by Medical Dictionary for Regulatory Activities (MedDRA; v21.1) system organ class and preferred term. One subject will be counted only once within one preferred term and one system organ class. The summary will be sorted in the alphabetic order of system organ classes and preferred terms.

Medical history details as collected on the electronic case report form (eCRF) such as body system, description, the date of onset, stop date and the current status of the condition will be presented in a by-subject data listing.

5.1.5. Prior and Concomitant Medications

Prior medications are defined as those taken before the date of the first study drug administration, i.e. started before the start of the study drug.

Concomitant medications are defined as any non-study medication taken during the treatment period which is from the date of first dose to the date of last dose plus 6 weeks.

Additionally, the medications will be considered concomitant if the start date of the medication is missing.

A medication that started prior to the first dose of the study drug and continued after that date will be considered as both prior and concomitant.

Prior and concomitant medications will be coded using World Health Organization (WHO) Drug (version March 2018). Medications will be summarized by ATC level 2 code and preferred term. Summary will be done by periods (i.e., RI, RW, and LTE) and by treatment (KPL-914 vs placebo) for RW period. One subject will be counted once within one preferred term and one ATC class. The medication information will be presented in a by-subject listing with ATC class (level 2) and WHO Drug Dictionary preferred term, start and stop date, dosage, route, frequency and indication.

Concomitant pericarditis treatment will be summarized by period and by treatment for RW period using the following categories:

- Analgesics
 - Non-opioid analgesics
 - Opioid analgesics
- Nonsteroidal anti-inflammatory drug (NSAIDs)
 - Aspirin
 - Other NSAIDs
- Colchicine
- Corticosteroids
 - Oral corticosteroids
 - IM/IV corticosteroids
- Other

In addition, concomitant pericarditis treatment received during the RW treatment period will also be summarized based on the status of receiving bailout treatment (i.e. concomitant

medication received before start of bailout treatment vs after start bailout treatment) for each treatment group in the RW period.

For RI period, use of concomitant pericarditis treatment (i.e., background treatment) will be summarized over time.

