2. STUDY DESIGN

2.1. Design Overview

This study has the following periods:

- **Screening period**, during which assessment of disease characteristics, baseline therapy, and the pretreatment workup is completed (up to 4 weeks).
- **Single-blind Run-In (RI) period** (12 weeks), during which blinded rilonacept is administered subcutaneously (SC) once weekly in all subjects after the loading dose of double injections. The RI period includes the following:
 - 1-week Stabilization period, during which blinded rilonacept is administered in addition to standard of care (SOC) pericarditis therapy and the ongoing pericarditis episode is treated.
 - 9-week Weaning period, during which subjects are weaned off background SOC pericarditis therapy, as applicable, while treatment with blinded rilonacept continues.
 - 2-week Monotherapy period during which subjects who have successfully weaned off background SOC pericarditis therapy will continue to receive blinded rilonacept.

In the single blind RI period (subjects are blinded regarding the time of transition from the single- blind to the double- blind- period), adult subjects ≥ 18 years old will receive rilonacept as an initial loading dose of 320 mg (2 SC injections of 160 mg each) at the RI baseline visit (2×2 mL), followed by a 160 mg (2 ml) SC dose once weekly throughout the RI period. Pediatric subjects (≥ 12 and < 18 years old) will receive an initial loading dose of rilonacept 4.4 mg/kg (2 SC injections of 2.2 mg/kg each) at the RI baseline visit (maximum 2×2 mL), and then 2.2 mg/kg (maximum 2 mL) SC once weekly throughout RI period.

Subjects who achieve clinical response at RI Week 12 defined as stopping background pericarditis therapy no later than Week 10 and weekly average of daily pericarditis pain score ≤ 2.0 on the 11-point Numerical Rating Scale (NRS) within the 7 days prior to and including the day of randomization on RI Week 12/Randomization Withdrawal (RW) baseline and a C-reactive protein (CRP) level ≤ 0.5 mg/dL at the RI Week 12/RW baseline visit, will proceed into the double-blind placebo-controlled RW period.

Subjects who do not achieve clinical response at RI Week 12/RW baseline on rilonacept monotherapy will be discontinued from study drug, transitioned to SOC pericarditis therapy at the Investigator's discretion and followed through the end of the RW period.

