13.2. Missing Data Imputation Rules

Partial missing dates will be imputed for start/stop dates of AE and prior/concomitant medications, as well as start date of each pericarditis episode according to the rules below.

Table 8: Imputation Rules for Partial Missing Dates

Category	Scenario	Rule for missing dates
General rule	All	If year is missing, do not impute, unless otherwise specified
AE and prior/concomitant medication start date	Day is missing and (month, year) same as the first dose date	The day will be imputed as the same day of the first dose day or stop date, whichever is earlier.
	Day is missing and (month, year) not the same as the first dose date	The day will be imputed as the first day of the month or stop date, whichever is earlier.
	Month and day missing, year the same as the first dose date	Date will be imputed with the first dose date or stop date, whichever is earlier.
	Month and day missing, year different from the first dose date	Impute with the first day of the year.
AE and prior/concomitant medication end date	Day is missing	Impute with min(last day of the month, data cutoff, end of study date)
	Day and month are missing	Impute with min(last day of the year, data cutoff, end of study date)
	Entirely missing	Impute with min(data cutoff, end of study date)
First pericarditis episode start date	Day missing	Use first day of the month
	Month missing	Use January 01
Second or later pericarditis episode start date	Day missing	Use max(first day of the month, stop day of previous episode +1)
	Month missing	January 01
Other	Non-specific	For missing data handling rules not covered in this table, they will be defined in the ADaM Define file.

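### SAP section 5.1.5 classes a medication with a wholly missing start date as concomitant even when its recorded stop date is before the first dose

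*SAP*

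**What the plan says.** Section 5.1.5 of SAP v2.0 first fixes the two classes. For prior use: "Prior medications are defined as those taken before the date of the first study drug administration, i.e. started before the start of the study drug". For concomitant use: "Concomitant medications are defined as any non-study medication taken during the treatment period which is from the date of first dose to the date" of the last dose plus 6 weeks. The next sentence extends the second class: "the medications will be considered concomitant if the start date of the medication is missing". Neither that sentence nor anything later in the section mentions the stop date as a limit on this extension.

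Section 13.2, Table 8, governs incomplete dates. Its general rule is "If year is missing, do not impute, unless otherwise specified", and none of the start-date rows specifies otherwise. Start dates with a known year are imputed. Three of the four start-date rows cap the imputed date at the stop date; the row for a missing month and day in the year of first dose, for example, reads "Date will be imputed with the first dose date or stop date, whichever is earlier".

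Stop dates are collected: the by-subject listing in 5.1.5 shows "preferred term, start and stop date, dosage, route, frequency and indication". Medications are tabulated by run-in (RI), randomized withdrawal (RW) and long-term extension (LTE), and by arm in RW. Pericarditis treatment in RW is also split at the start of bailout. SAP v1.0 has the same missing-start sentence.

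**The concern.** The missing-start sentence contradicts the definition directly before it. A course that ended before the first dose was not taken between first dose and last dose plus 6 weeks, whatever its start date. When the stop date is on file, the class is known, yet the rule assigns the opposite one.

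A default towards concomitant is sensible when timing is unknown. Here it is not unknown. Table 8 already uses the stop date to limit partial start dates and ignores it only when the start is wholly missing, which looks like an oversight rather than a choice.

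At stake is the accuracy of the concomitant-medication tables, including the rows for analgesics, NSAIDs, colchicine and corticosteroids. Old courses with an unknown start year would be counted there as use on study.

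**Working it through.** No figure in the SAP rests on this rule, so there is none to reproduce. The check applies the rules to test records.

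**Step 1: which records reach the rule.** A record does so only if its start date is still missing after Table 8. Dates with a known year are imputed; dates with no year are not. So only wholly missing start dates are affected.

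**Step 2: classify six records.** The dates are invented for the test: first dose 15 March 2019, last dose 1 December 2019. The stop-date check keeps a missing-start record as concomitant only if it is ongoing or its stop is on or after first dose.

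| Start recorded | Stop | Start after Table 8 | Class under 5.1.5 | Class with stop-date check |
|---|---|---|---|---|
| wholly missing | 1 June 2018 | missing | concomitant | prior only |
| wholly missing | 1 May 2019 (in RI) | missing | concomitant | concomitant |
| wholly missing | ongoing | missing | concomitant | concomitant |
| 2019 | 1 February 2019 | 1 February 2019 | prior | prior |
| March 2019 | 10 March 2019 | 10 March 2019 | prior | prior |
| 2018 | 1 June 2018 | 1 January 2018 | prior | prior |

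One of the six changes class: wholly missing start with a stop before first dose. If prior use is programmed from the start date, as its definition suggests, this record is also lost from the prior table, because there is no start date to test.

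**Step 3: assignment to periods.** Section 5.1.5 has no rule saying which of RI, RW or LTE receives a medication with no start date. The bailout table is limited to treatment received in the RW period, which would exclude a drug with an earlier recorded stop. For the other tables the SAP is silent.

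**Step 4: size per subject.** Section 2.3.1 plans about 56 enrolled and about 25 randomized per arm, and expects no more than 100 enrolled. One misclassified subject adds to a drug-class row:

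- over all enrolled: 1/56 = 1.8 percentage points, or 1/100 = 1.0 point at the upper limit;
- in one RW arm, only if the record is carried into RW: 1/25 = 4 points.

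Each figure also requires that the subject has no genuine use in that row.

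**The case against.** The best defence is that the word introducing the sentence marks it as a deliberate, conservative extension for unknown timing, and that Table 8 sends uncovered missing-data rules to the ADaM Define file. The first part stands for records whose stop is unknown or ongoing, and the fix keeps it there. It does not stand for a recorded stop before first dose, where the timing that matters is known. The second part may cover period assignment, but the classification itself is stated outright in 5.1.5 and is not an uncovered case.

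A reader might infer more than the text supports:

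- *That any incomplete start date triggers the problem.* Dates with a known year are imputed, and all three such test records were classified correctly.
- *That a stop before randomization is also a contradiction.* The treatment period begins at first dose in RI. Background therapy is weaned during RI, not washed out before it, so a drug stopped in RI is properly concomitant.
- *That old therapy will show up as RW use in subjects who entered RW by "stopping background pericarditis therapy no later than Week 10".* No sentence in the SAP places missing-start drugs in RW. The silence permits it; it does not require it.
- *That monotherapy or rescue results are distorted.* These have their own definitions: off-background status in 5.2.3.1 (endpoints 3 and 18), Week 16 response in 5.2.2.1, and rescue use in 5.2.2.3 (endpoints 24 and 25). None refers to the 5.1.5 flag. The listing also lets a reader see a stop before first dose.

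**Conclusion.** The point holds in narrow form. A medication with unknown start year and a recorded stop before first dose is classed as concomitant, against the SAP's own definition. This is a stated rule giving a wrong class, not a missing detail.

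Its weight is minor. It can inflate descriptive concomitant-medication tables only; no primary, responder or rescue endpoint is tied to the flag. The SAP does not give the number of affected records, so the total effect cannot be estimated. It is zero if no record combines an unknown start year with a stop before first dose. The per-subject figures assume the planned sample size and no other use by that subject in the same row.

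**What to change.** Replace the missing-start sentence in 5.1.5 with: *A medication with a missing start date will be considered concomitant unless its stop date (after imputation) is before the first dose of study drug, in which case it is prior only.*

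Add that the same check applies when such records are assigned to the RI, RW (before and after bailout) and LTE summaries, so that a medication that stopped before a period began is not counted in that period.

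A record with neither start nor stop known would still count as concomitant, possibly in more than one period. That is an acceptable default, because nothing on file contradicts it.

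The cost is one sentence of SAP text, one clause on periods and one programming condition. No new data are needed, because stop dates are already collected and wholly missing ones are imputed under Table 8.

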5.1.6. Study Drug Administration

The study medication administration details including the administration date and time, dose, site of injection and comments will be presented in a by-subject listing.

The following parameters related to study drug administration will be summarized for each of the treatment periods: RI, RW, LTE, and Study Overall.

- Treatment duration in weeks:
 - For RI period, it is defined as [minimum of (date of last study drug +6, date of RI week 12 visit – 1, date of data cutoff) - date of first study drug + 1)/7].
 - For RW period it is defined as [minimum of (date of last study drug +6, date of end of RW visit) - date of first study drug + 1)/7].
 - For LTE and study overall, it is defined as [minimum of (date of last study drug +6, end of study date, date of data cutoff) - date of first study drug + 1)/7].

Number of administrations in each period regardless of full amount or partial amount of syringe injected. The loading dose includes two injections and will be counted as one administration.

Compliance (%) in each period, calculated as (number of administrations) / (protocol planned number of administrations) × 100%. The loading dose includes 2 injections and will be counted as one administration.

Total riloncept dose administered in each period, defined as the sum of all doses (mg) received in the corresponding period. The actual volume administered will be used to calculate the total dose. For subjects receiving weight-adjusted dose (e.g., 2.2 mg/kg) their weight collected at scheduled visits will be used to calculate the amount of the study drug received.

Percentage of self-administrations by the subject, defined as [Number of self-administrations] / [Total number of administrations received] × 100%. The loading dose will be included in the denominator as one administration. If one of 2 injections in the loading dose is self-administered, it will be counted in the numerator.

5.1.7. Protocol Deviations

Protocol deviations will be derived programmatically as well as reported by sites.

A blinded review before database lock will be conducted to determine important protocol deviations. Protocol deviations are considered important if based on Sponsor assessment they can impact study integrity or interpretability of study results.

Important protocol deviations will also be evaluated if they have impact on efficacy data. Important protocol deviations with potential impact on efficacy will be used to exclude subjects from PP analysis set.

All protocol deviations will be reviewed and categorized before database lock. All important protocol deviations will be summarized by deviation category (including Inclusion Criteria,

Exclusion Criteria, ICF, Concomitant Medication, and other if applicable). The protocol deviation data will also be presented as a by-subject data listing.

5.2. Efficacy Analysis

5.2.1. Primary Efficacy Endpoint

5.2.1.1. Definition

The primary efficacy endpoint is time to pericarditis recurrence, defined as the time from randomization to the date of the first pericarditis recurrence for each subject. Only CEC-confirmed pericarditis recurrence will be considered as an event for the primary analysis.

Time to pericarditis recurrence is calculated as: Data of Event/Censor – Date of randomization +1.

Pericarditis recurrence is defined as the recurrence of typical pericarditis pain associated with supportive objective evidence of pericarditis. The assessments to be conducted by the investigator is described in protocol Section 6.1.4. At any time during the RW period, subjects who experience a suspected recurrence of pericarditis symptoms will be requested to report to the study site/clinic for a scheduled or unscheduled visit, during which clinical assessments will be performed to gather all the necessary diagnostic data to confirm or rule out the presence of pericarditis recurrence.

Pericarditis recurrence will also be evaluated by the investigators at the following time points:

- Routine assessment (every 4 weeks until week 24 in RW, then every 8 weeks)
- End of RW period
- End of treatment
- Post-treatment safety follow-up
- LTE assessment (every 12 weeks up to 24 months and 18-month visit)

Upon suspected pericarditis recurrence, the event is required to be captured in the electronic data capture (EDC) system within 24 hours of learning of the event, and a pericarditis recurrence event adjudication package must be prepared for adjudication by CEC. Details on endpoint package requirements will be described in the CEC charter. The CEC confirmed pericarditis recurrences will be used for the analysis of primary efficacy endpoint.

The censoring rules in [Table 1](#) will be used in the analysis of the primary efficacy endpoint, in which, the event/censor reason will be provided in a data listing.

Table 1: Censoring Rules for Time to Pericarditis Recurrence in the RW Period

	Scenario*	Event/ Censor	Event/Censor Reason	Date of Event/ Censor
1	Pericarditis recurrence occurred before or without receiving bailout rilonacept, including events after termination of study drug	Event	Recurrence	Date of pericarditis recurrence
2	Pericarditis recurrence occurred after receiving ORT* or corticosteroid	Event	Recurrence after receiving ORT/corticosteroid	Date of pericarditis recurrence
3	Receiving bailout rilonacept before pericarditis recurrence	Event	Recurrence after receiving bailout	Date of pericarditis recurrence
4	No pericarditis recurrence during RW period with or without receiving ORT/corticosteroid	Censored	No pericarditis recurrence	Date of last assessment for pericarditis recurrence on or before data cutoff.

*Excluding subjects receiving ORT/corticosteroid while waiting for at least 5 days since previous administration of study medication before receiving bailout rilonacept or within 5 days prior to recurrence visit.

